3.1.3 Moderation analysis

We plan to explore treatment effect moderation on the primary outcome of viral suppression at 12 months post-randomisation, and the secondary outcomes of self-report adherence and PHQ-9 depression by the putative moderator sex. We will assess moderation separately for each outcome as follows. We will add the sex variable to all models, then will add a sex by trial arm interaction term to the primary viral load outcome model, and a sex by trial arm by time term to the self-report adherence model. For PHQ-9 depression, we will have only a sex by trial arm term and will not include time in the interaction term in order to provide the average treatment difference over the outcome period. There will be considered to be moderation if the overall interaction term p-value is less than 0.05. If sex is a significant moderator, in addition to presenting overall treatment effects as per Sections 3.1.1 and 3.1.2, we will also present treatment effects by levels of the moderator.

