3.1.2 Analysis of secondary outcomes

The mean difference at 12 months (and associated 95% CI) in PHQ-9 between TENDAI and EUC, and a standardised effect size, will be estimated using a linear mixed effects model with the 4, 8 and 12 month measures as dependent variables; a random intercept at the participant level, with a random slope if warranted (assessed via likelihood ratio test); baseline PHQ-9, trial arm, time, and trial arm by time interaction terms as independent variables; as well as the site stratification variable. Note for this PHQ-9 outcome that while we will include all post-randomisation measures as dependent variables in the model in order to account for missing data, we will not present treatment difference estimates for 4 and 8 months (as per the trial objectives/outcomes).

Pharmacy refill data will be recoded into a binary variable: greater than or equal to 90% adherence in the past month or less than 90% adherence in the past month. Please refer to Appendix 1 – Scoring of outcome measures. The odds ratio at 4, 8 and 12 months (and associated 95% CI) for ≥90% pharmacy refill adherence between TENDAI and EUC will be estimated using a logistic mixed effects model with the 4, 8 and 12 month measures as dependent variables with a random intercept at the participant level, consideration of a random slope variable and similar independent variables as those described for PHQ-9. Please see the end of the section for some further details on the modelling of this binary variable.

Self-report adherence (Wilson et al) will be scored as described in the paper and modelled as described for PHQ-9.

The mean difference in log copies/mL of viral load at 12 months (and associated 95% CI) between TENDAI and EUC will be estimated using a linear regression model with the log viral load at 12 months as the dependent variable,

baseline log viral load and trial arm as independent variables, as well as the site stratification variable. Undetectable viral loads will be set to half the viral detection load limit of the Marondera Provincial Hospital lab machine, which is 15.

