3.1.4 Statistical considerations

3.1.4.1 Time points

Outcomes are measured at months 4,8, and 12 months after randomisation. Follow-up visits should be completed at no more than 1 month before the expected visit and at no more than 2 months after. We will plot histograms of the time post-randomisation of the visits and will report the proportion of research follow-up visits which are outside of the expected visit window by trial arm and assessment time point. The time windows will be summarised descriptively using means and standard deviations or medians and interquartile ranges as appropriate. There are no set time windows for the acceptable time window for the time from baseline to randomisation and from randomisation to start of treatment.

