3.2 Planned subgroup analyses

No formal subgroup analyses are intended as the study is not powered to detect treatment effects for subgroups.

However, we do plan to explore treatment effect moderation on the primary outcome of viral suppression at 12 months post-randomisation, and the secondary outcomes of pharmacy refill adherence, self-report adherence and PHQ-9 depression (all at 12 months) by the putative moderator, sex – please see section 3.1.3.

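### In SAP 3.1.3 the sex-moderation rule for self-report adherence rests on a sex by arm by time term, which as written tests change in moderation over visits and cannot detect a sex difference that is the same at every visit

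*SAP*

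**What the plan says.** SAP 3.1.3 examines whether sex modifies the treatment effect on three outcomes, and the interaction differs between them:

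- **Viral suppression:** a sex by arm term.
- **Self-report adherence:** the plan adds sex, "and a sex by trial arm by time term to the self-report adherence model".
- **PHQ-9:** a sex by arm term only; the plan "will not include time in the interaction term in order to provide the average treatment difference over the outcome period".

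The decision rule is common to all three: "There will be considered to be moderation if the overall interaction term p-value is less than 0.05". If sex passes that test, "we will also present treatment effects by levels of the moderator"; otherwise no by-sex estimates are promised.

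The model that receives the three-way term is set out in SAP 3.1.2. Self-report adherence is "modelled as described for PHQ-9", that is, a linear mixed model on the 4-, 8- and 12-month measures with "baseline PHQ-9, trial arm, time, and trial arm by time interaction terms as independent variables" (the adherence baseline taking the place of the PHQ-9 one) and site.

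SAP 3.2 describes the same moderation work differently. It covers viral suppression at 12 months "and the secondary outcomes of pharmacy refill adherence, self-report adherence and PHQ-9 depression (all at 12 months) by the putative moderator, sex", and refers back to 3.1.3 for the method.

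**The concern.** Once a model holds the two-way terms, a three-way term carries only the part of the sex by arm effect that varies with time. A benefit on adherence seen in one sex and not the other, to the same extent at each visit, is the simplest form that moderation could take. All of it sits in the sex by arm term, which the stated rule does not name for this outcome.

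The consequence lies in reporting. Sex is the one moderator kept for the main paper (SAP 1.8.5), and by-sex estimates depend on significance. A stable sex difference in the adherence effect would then usually be reported as no moderation, with no estimates by sex from which a reader could judge.

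The two SAP sections also lead to different analyses. Section 3.2 fixes 12 months. Section 3.1.3 gives a change-over-time test for adherence and an average over follow-up for PHQ-9, and neither is a 12-month contrast. Pharmacy refill is listed as an outcome for moderation in 3.2 but not in 3.1.3, nor in SAP 1.1 or 1.8.5.

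**Working it through.** **Inputs from the documents.** 290 randomised 1:1 with 20% attrition (SAP 1.9): 290 × 0.8 / 2 = 116 per arm, 232 in all. About 60% female (protocol section 9): 70 women and 46 men per arm. Visits: "Outcomes are measured at months 4,8, and 12 months after randomisation". Two-sided 5% level.

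**Assumptions not in the documents.** Outcome SD 1 at each visit; equal correlation ρ between visits, 0.3 to 0.7; a sex difference d in the treatment effect, in SD units, the same at each visit; time categorical; no gain from baseline adjustment.

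**The plan's own figure.** The documents give no power for the moderation test. The primary power statement (45% against 65%, Fisher's exact test) reproduces at 85.0% by exact enumeration with 116 per arm, against the stated 85%, so 232 is the right evaluable number.

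**Step 1: the three-way term.** Let δ4, δ8 and δ12 be the sex differences in treatment effect at the three visits. With the lower-order terms in the model, the three-way coefficients are δ8 − δ4 and δ12 − δ4 (2 df). If δ4 = δ8 = δ12 = d, both are zero, the noncentrality is exactly 0, and the rejection rate is 5.0%. That holds for d = 0.3, 0.5 or 0.8 and any ρ. It is algebra and does not depend on the assumed values.

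**Step 2: sex by arm averaged over visits.** The variance of a person's three-visit mean is (1 + 2ρ)/3, so

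SE = √[ (1 + 2ρ)/3 × (2/70 + 2/46) ], with 2/70 + 2/46 = 0.07205.

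For d = 0.5:

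- ρ = 0.3: SE = √(0.5333 × 0.07205) = 0.196; 0.5/0.196 = 2.55; power 72%.
- ρ = 0.5: SE = √(0.6667 × 0.07205) = 0.219; 0.5/0.219 = 2.28; power 63%.
- ρ = 0.7: SE = √(0.8 × 0.07205) = 0.240; 0.5/0.240 = 2.08; power 55%.

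**Step 3: joint 3-df test of sex by arm plus the three-way term.** For a constant d the noncentrality is the square of the ratio in Step 2 (6.51, 5.20, 4.34), now referred to chi-square on 3 df: power 56%, 46%, 39%.

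**Step 4: 12-month contrast.** SE = √0.07205 = 0.268; 0.5/0.268 = 1.86; power 46%, whatever ρ.

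**Step 5: other sizes of d, at ρ = 0.5.**

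| d (SD) | Three-way (2 df) | Averaged (1 df) | Joint (3 df) | 12 months (1 df) |
|---|---|---|---|---|
| 0.3 | 5% | 28% | 18% | 20% |
| 0.5 | 5% | 63% | 46% | 46% |
| 0.6 | 5% | 78% | 62% | 61% |
| 0.8 | 5% | 96% | 88% | 85% |

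**Step 6: the literal omnibus.** If the three-way term is added to the base model plus sex, with no separate sex by arm or sex by time term, it absorbs both. A test of the whole block then has 2 (sex by time) + 1 (sex by arm) + 2 (three-way) = 5 df. At d = 0.6 and ρ = 0.5 the noncentrality is 0.36/0.04803 = 7.5 and the power 53%. This test would also react to a sex difference in time trend common to both arms, which is not moderation.

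**The case against.** The strongest reply is that the 5% figure belongs to a model that the SAP does not write out in full. Section 3.1.3 does not say that a separate sex by arm term is fitted and left out of the test, and the word *overall* in the decision rule could mean a joint or omnibus test. On those readings a constant difference can be detected (62% for the joint test, 53% for the literal block, at 0.6 SD and ρ = 0.5). This stands as an ambiguity. It does not rescue the rule: no joint test is stated, time was kept for adherence while it was expressly dropped for PHQ-9, and the literal block would mix in sex by time.

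A second reply is that the analysis is exploratory and that SAP 3.2 says the trial is not powered for subgroups. That is correct and limits the severity. It does not justify a test with only its false-positive rate against the simplest form of moderation.

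A third is that averaging for PHQ-9 was a deliberate choice with its reason given. That also stands. The average is the more powerful contrast under a constant difference (78% against 61% at 12 months, for 0.6 SD and ρ = 0.5), and the only difficulty is that 3.2 says otherwise.

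A reader might infer that the paper's statement on sex and adherence will be wrong, or that the plan forgoes 78% power for 5%. The documents support neither. The first needs a stable sex difference to exist and the narrow reading to be followed; the test does respond to moderation that varies over visits. The second rests on an assumed difference of 0.6 SD and correlation of 0.5, and 78% belongs to the averaged test, not to a joint one.

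**Conclusion.** The point holds in a limited form. On the plain reading of SAP 3.1.3, the adherence moderation rule tests whether moderation changes across visits, and it rejects at 5% for any sex difference equal at 4, 8 and 12 months. On the alternative readings the test is unstated, and one of them is also wrong. For a constant 0.5 SD difference the usable alternatives have 39% to 72% power, depending on the contrast and the correlation. Those figures rest on an assumed effect size, correlation structure and SD; the 5% does not. Separately, 3.1.3 and 3.2 disagree on time point and on whether pharmacy refill is included, whichever reading is taken. Severity is low: one exploratory analysis of one secondary outcome is affected, and the primary result and the overall secondary effects are untouched.

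**What to change.** 1. **Self-report adherence.** Fit sex by arm, sex by time and sex by arm by time, and base the moderation decision on one named sex by arm contrast. This can be the average over visits, as already chosen for PHQ-9, or the 12-month contrast that SAP 3.2 implies. Report the three-way term only as a test of change over time.
2. **PHQ-9.** The averaged test may stay, provided that 3.2 is aligned with it.
3. **Sections 3.1.3 and 3.2.** Give the same time point and the same outcomes in both: either drop pharmacy refill from 3.2, or add it to 3.1.3 with its model.

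The cost is SAP wording and a contrast statement in the code; no new data are needed. The choice of contrast involves a trade. The average is more powerful if the difference is stable, while the 12-month contrast matches 3.2 but has less power (46% against 55% to 72% at 0.5 SD).

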3.1.4 Statistical considerations

3.1.4.1 Time points

Outcomes are measured at months 4,8, and 12 months after randomisation. Follow-up visits should be completed at no more than 1 month before the expected visit and at no more than 2 months after. We will plot histograms of the time post-randomisation of the visits and will report the proportion of research follow-up visits which are outside of the expected visit window by trial arm and assessment time point. The time windows will be summarised descriptively using means and standard deviations or medians and interquartile ranges as appropriate. There are no set time windows for the acceptable time window for the time from baseline to randomisation and from randomisation to start of treatment.

3.1.4.2 Stratification and clustering

Randomisation will be stratified by site and the randomisation stratifier will be included in all models as a covariate.

For some data, the data structure is longitudinal with repeated measures for continuous and binary outcomes (see table 5.1 for details). The correlation of observations within participants will be accounted for by using mixed effects models with a random intercept at the participant level (or possibly generalised estimating effects models) as per Section 3.1.

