3. Third we will provide no-cost treatment of the intervention components to each participant in the control condition who wants it when they have completed their 12 month follow up assessment.

These three enhancements of usual care will be supported by the increasing availability more generally of antidepressants in general health care. Also, awareness of depression treatment is increasing in Zimbabwe, following the rollout of the Friendship Bench, a lay-health worker delivered stepped-care program for depression in three cities.

**Intervention Group - Stepped Care-AD.** Those randomized into stepped care-AD will receive problem solving therapy for adherence and depression (PST-AD) over 6-weekly sessions, delivered by adherence counselors. The stepped care-AD will be delivered by adherence counsellors specifically trained in the intervention, who do not provide routine care and will take place in a separate building to the EUC counselling. This is to reduce the risk of contamination between the two arms, by increasing the privacy of the stepped care-AD intervention sessions, and preventing awareness of the stepped care-AD intervention impacting the counselling the EUC participants receive. Participants will be considered to have completed the intervention after finishing 4 or more sessions. To reduce participant attrition, sessions 4, 5 and 6 may be conducted by telephone for participants who are unable to travel to the clinic (for example if participants cannot travel to the clinic because of C-19 lockdown travel restriction). The 6 TENDAI sessions are as follows:

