### **Understanding the priorities, enablers and barriers of implementing the TENDAI intervention (PST-AD) for people living with HIV and depression in Zimbabwe**

Qualitative methods informed by implementation science frameworks will be used to understand participant experience of receiving the intervention, and enablers and barriers of implementing the TENDAI intervention.

The aim of this sub-study is to a) explore participant's response to the intervention and b) gather evidence to inform a future implementation study of the TENDAI intervention. This will be achieved by identifying relevant implementation science frameworks and using qualitative methods to understand the context of implementation, implementation priorities, and barriers and facilitators, to inform an implementation strategy.

Approximately 45 participants will be recruited. This will be 30 adults who have received the intervention, 4 interventionists and 11 health care providers and policy makers. All participants will complete informed consent procedures. The topic guide(s) have been informed by key implementation science frameworks. Participants who have received the TENDAI intervention will be invited to take part in the exit interviews at 4 or 8 month post randomization follow up. The first half of the interviews with participants who have received the TENDAI intervention will focus on understanding patient's experience of receiving the intervention and response to the intervention. The second half will focus on understanding the context of implementation including individual level barriers and facilitators. Interviews with health care workers, policy makers and interventionists will focus on understanding the context of implementation including barriers and facilitators.

Interviews will be audio recorded and will be translated and transcribed for analysis.

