**Reliability of diagnostic and efficacy ratings.** Inter-rater agreement will be assessed via evaluation of audiotapes of baseline pre-randomization diagnostic interviews which includes the PhQ-9. Inter-rater reliability (kappa) will be calculated for each of the diagnostic categories. A minimum of 15 Independent Assessor audio recordings from the first follow-up visit will be scored on competency by a study clinician who was not involved in the visit, and measures of

concordance (e.g., intra-class correlation coefficient for continuous measures and kappa for dichotomous measures) will be calculated. Discrepancies in scoring will prompt discussion and recalibration of clinician administered assessment procedures as necessary. To prevent observer drift, periodic recalibration of raters will be carried out using reliability assessment data.

**Therapy training.** The therapy manual developed and adapted in the R21 by the current study team will be used. The local Clinical Psychologist will be the primary supervisor of the adherence counsellors, and will be supervised by [name] (the site PI) [name] and the research psychologist (MGH) will support [name] and the local clinical psychologist, through weekly phone calls and video calls and at least twice annual site visits to provide in-person training the study adherence counsellors, who conduct the intervention, and their supervisors.

**Therapy supervision.** Supervision of study therapists will take place on a weekly basis. The Zimbabwe Programme Manager has primary responsibility for ensuring weekly supervision of the adherence counsellors.

**Assessment of intervention integrity.** The therapy adherence measure will assess the extent to which therapy activities were implemented in a manner that is maximally consistent with the intent of the therapy manual. All treatment sessions will be recorded and a random selection of 10% of sessions for each therapist will be translated (orally) and rated by the clinical psychologist and the Zimbabwe Programme Manager.

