1.9 Sample size estimation

A sample size of 290 participants will provide 85% power to detect an absolute difference of 20% or more in achieving viral suppression (e.g. 45% in the EUC arm vs. 65% in the intervention arm) at 12-months follow-up. This is based on a two-sided Fisher's exact test with $\alpha = 0.05$ and allowing for 20% attrition. Pilot data showed a larger difference between arms (50% in the EUC arm vs. 75% in the intervention arm), suggesting this should be a conservative sample size estimate. For the secondary outcomes, this sample size will allow detection of an effect size of 0.37 or greater on the continuous depression scale (based on $\alpha = 0.05$, a two-sided test of difference between two independent means and the same level of attrition). The sample size will also provide 90% power to detect a 20% difference in the proportion with $\geq 90\%$ adherence as was seen in our pilot data (also Fisher's exact test, $\alpha=0.05$ and 20% attrition). This is based on our pilot data, national data (Dube et al) and other research (Ciesla et al, Safran et al).

2. Data analysis plan – Data description

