3.1 Main analysis of treatment differences

The main statistical analyses will follow the intention to treat principle as much as possible. The senior statistician will remain fully blind until an initial draft of the primary analysis report is complete and needs to be checked. The trial

statistician will be unblinded. Group difference estimates between TENDAI and EUC and associated 95% confidence intervals will be reported from models appropriate to the measurement schedules and nature of the outcome in question, i.e. depending on whether the outcome is continuous or categorical. The models that will be used are outlined in the following sections. Where the outcome variable is recorded at baseline it will generally be included in the analysis model as a covariate unless stated otherwise. The significance level for the difference between TENDAI and EUC on the primary outcome will be 5% (two-sided). This significance level will also be used for the secondary outcomes, but the reader will be alerted regarding the impact of multiple testing.

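### No SAP model lets outcomes vary by TENDAI counsellor, so confidence intervals are too narrow for inference beyond the counsellors employed if such variation exists

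*SAP*

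**What the plan says.** Protocol 11a: "The stepped care-AD will be delivered by adherence counsellors specifically trained in the intervention, who do not provide routine care". Sessions are individual: six weekly, then a booster (Protocol 13). Enhanced usual care (EUC) is also given individually, but by counsellors or nurses of the health facility who are not trained in TENDAI (Protocol 11a). The two arms therefore have separate sets of providers.

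SAP 3.1.4.2, the section on stratification and clustering, includes site as a covariate in every model. For repeated outcomes it states: "The correlation of observations within participants will be accounted for by using mixed effects models with a random intercept at the participant level", with GEE as a possible alternative. SAP 3.1.1 analyses viral suppression at 12 months by logistic regression on arm and site, and repeats it with baseline log viral load. SAP 3.1.2 analyses log viral load by linear regression. Neither of these two models has a random effect. The robust standard errors for the pharmacy-refill GEE models serve the repeated measures.

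The sample size (SAP 1.9, Protocol 14) treats participants as independent: "A sample size of 290 participants will provide 85% power to detect an absolute difference of 20% or more in achieving viral suppression". Neither document contains a counsellor effect, an ICC, a design effect or a sensitivity analysis for clustering.

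**The concern.** Participants who share a counsellor may have outcomes that are more alike than those of participants with different counsellors. If so, the TENDAI arm holds less information than its headcount suggests, and a model that treats its members as independent reports too small a standard error. A site term cannot represent differences between counsellors at the same site.

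This matters because of what the trial wants to conclude. The protocol presents it as an effectiveness trial in a real-world setting, lists representative usual providers among its design criteria (Table 1), and argues for task-shifting so that an effective intervention can be scaled up (6a). Those conclusions concern counsellors in general, not only those hired here. A primary result close to p = 0.05 would then be open to a challenge that the plan gives no agreed way to answer.

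**Working it through.** **Inputs from the documents.** 290 randomised 1:1, "allowing for 20% attrition": 290 × 0.8 = 232 analysed, 116 per arm. Rates: "45% in the EUC arm vs. 65% in the intervention arm". Two-sided 5% level.

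**Assumptions.** The documents give neither the number of counsellors k nor the ICC. I take k = 4 to 8 and ICC = 0.01 to 0.05, with equal caseloads m = 116/k and clustering in the TENDAI arm only.

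**The plan's own figure.** Exact two-sided Fisher power at 116 per arm, 45% against 65%, is 85.0%. The stated 85% reproduces.

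**Standard error and error rate.** Design effect in the TENDAI arm: DE = 1 + (m − 1) × ICC. With equal variances in the arms, true SE / reported SE = R = √[(1 + DE)/2]. Actual two-sided error = 2 × [1 − Φ(1.96/R)].

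Worked case, k = 4 and ICC = 0.05: m = 29, DE = 1 + 28 × 0.05 = 2.40, R = √1.70 = 1.30, 1.96/1.30 = 1.50, error 13.3%.

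| k | ICC | DE | R | Two-sided error |
|---|---|---|---|---|
| 4 | 0.01 | 1.28 | 1.07 | 6.6% |
| 4 | 0.02 | 1.56 | 1.13 | 8.3% |
| 4 | 0.05 | 2.40 | 1.30 | 13.3% |
| 8 | 0.01 | 1.14 | 1.03 | 5.8% |
| 8 | 0.02 | 1.27 | 1.07 | 6.6% |
| 8 | 0.05 | 1.68 | 1.16 | 9.0% |

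A beta-binomial simulation of the unadjusted log odds ratio test (40,000 runs) gave errors of 7.3%, 9.0% and 14.2% for k = 4 and 6.4%, 7.4% and 9.6% for k = 8. With the ICC near zero it gave 5.4% and 5.6%, so the formula and the simulation agree on the size of the increase. As an approximation, the same R applies to the PHQ-9 mean difference.

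**Power of the planned test.** It keeps the reported standard error, so power = Φ[(0.20 − 1.96 × SE_rep)/SE_true].
- SE_rep = √[(0.45 × 0.55 + 0.65 × 0.35)/116] = √(0.475/116) = 0.0640. With no clustering: Φ(0.20/0.0640 − 1.96) = 88%. This Wald formula runs above Fisher's 85%.
- k = 4, ICC 0.01: SE_true = √[(0.2475 + 0.2275 × 1.28)/116] = 0.0682, power 86%.
- k = 4, ICC 0.02: SE_true = 0.0721, power 85%.
- k = 4, ICC 0.05: SE_true = 0.0827, power 82%.

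A different test, one that uses the inflated standard error, has power Φ(0.20/SE_true − 1.96): 84% at ICC 0.01 and 68% at ICC 0.05 with k = 4.

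**Can the trial estimate the ICC?** With 4 counsellors of 29, a one-way ANOVA estimate is zero or negative when F on 3 and 112 degrees of freedom falls below 1. The probability of this is P[F(3,112) < (1 − ICC)/DE]: about 49%, 40% and 24% at true ICC 0.01, 0.02 and 0.05.

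**The case against.** **The sample size might seem wrong, with power as low as 68%.** A reader might infer this, but the documents do not support it. The stated 85% is correct under independence, and the planned test keeps about 86% to 82% with 4 counsellors. The 68% belongs to a test the SAP does not plan. What suffers is the width of the interval and the error rate.

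**The 5% test might seem to exceed 5% in all circumstances.** It does not. If TENDAI has no effect with any counsellor, the planned test is valid. The excess arises when counsellors' effects differ and average to zero over a wider population of counsellors. The claim is therefore limited to inference beyond those employed.

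**The protocol might seem to expect counsellors to differ, or to employ four.** It says neither. It rates "a random selection of 10% of sessions for each therapist", but that is integrity monitoring, and its training to set criteria, weekly supervision and feedback aim to reduce differences. The only count is in the implementation sub-study: "30 adults who have received the intervention, 4 interventionists and 11 health care providers and policy makers". Those four are interviewees, and Protocol 8 names both counsellors and nurses as interventionists. Nor do the documents say that a participant keeps one counsellor throughout.

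**The ICC for the primary outcome may be small.** Viral load at 12 months is a laboratory measure taken about nine months after the 12-week booster, and it also depends on drug resistance. This stands: 0.05 is an assumption, and at 0.01 the error is only 5.8% to 6.6%.

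**EUC participants also share providers.** This stands too. Treating EUC as unclustered is a simplification that needs stating.

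**A random-effect model can falsely reassure.** With few counsellors it will often return a zero ICC and nearly the original interval. This stands and shapes the fix.

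**Conclusion.** The point holds as a conditional omission. No planned model allows for counsellor, so any within-site counsellor effect makes the reported intervals too narrow for the generalisation the trial aims at. On the assumed ranges the standard error is understated by a factor of 1.03 to 1.30, and the error of the planned test lies between 5.8% and 13.3%. With an ICC near zero nothing of note changes. These figures use normal critical values, equal caseloads and an unclustered EUC arm. There is no arithmetic error in the plan and no case for changing the sample size. A pre-specified sensitivity analysis is worth adding because it is cheap and would settle the question before results are known.

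**What to change.** Amend SAP 3.1.4.2 before the primary analysis starts, adding a sensitivity analysis for viral suppression and PHQ-9 that:

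- (a) reports the number of TENDAI counsellors and the participants per counsellor, with a rule for participants seen by more than one;
- (b) fits a counsellor random effect in the TENDAI arm, with a small-sample correction for both outcomes, and reports the ICC;
- (c) shows the main treatment-effect interval with its standard error multiplied by √[(1 + DE)/2] at fixed ICC values, for example 0.01, 0.02 and 0.05, using the observed caseloads.

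The section should also say that clustering by EUC provider is not modelled, or include it if provider identity is recorded. The main model and sample size are unchanged.

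The cost is a paragraph of SAP text, two extra models and a small table. Counsellor identity is probably available, since therapist records are kept and sessions are sampled per therapist, but no counsellor identifier is listed as a data item, so this should be confirmed first. The downside is an imprecise ICC, so the result belongs beside the main analysis and not in place of it.
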